3.3 Secondary Study Endpoints

The secondary endpoint would be to more accurately plan the resection of mandibular or maxillary bone if invasion is predicted. If invasion is not predicted based upon the imaging modalities, then the secondary endpoint would be to spare resection of uninvolved bone

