2.0 STUDY OBJECTIVES

2.1 Primary Objective:

To determine which imaging modality or combination of imaging methods, in conjunction with clinical and histological examination, will most accurately predict the presence or absence of invasion of the mandible or maxilla by intraoral squamous cell carcinoma (SCC).

2.2 Secondary Objective:

To compare the histopathologic findings to the radiologic findings

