3.2 Primary Study Endpoints

The primary endpoint is to determine if any one or combination of imaging modalities can accurately predict the presence or absence of bone invasion by oral squamous cell carcinoma

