5.4 Method for Assigning Subjects to Treatment Groups

This study will not be randomized. All patients will received a helical CT, PET/CT and CBCT

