7.2 Statistical Methods

Sensitivity and specificity of the clinical exam, CBCT, helical CT, PET/CT, MRI and any other imaging modality used in detection of bone invasion will be calculated, as compared to the histological examination of the specimens.

Sensitivity: $[TP / (TP + FN)] \times 100$

Specificity: $[TN / (FP + TN)] \times 100$

Also, the confidence interval will be determined for the sensitivity and specificity.

True positive (TP): pts with histologic and radiographic evidence of invasion

True negative (TN): pts without histologic or radiographic evidence of

invasion

False Positive (FP): pts with positive radiologic evidence of invasion without histologic evidence

False Negative (FN): Those without radiographic evidence of invasion, but with histologic invasion present

In addition, the positive and negative predictive value will be calculated for each modality using the true positive and negatives as well as false positive and negative values.

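### The bone-sparing endpoint in 3.3 cannot be verified by this design, and 7.2 with 7.3 lets scan-negative patients without bone histology count as true negatives

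*Combined protocol and SAP*

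**What the plan says.** Section 3.3 holds the protocol's only secondary endpoint, in two branches. The first reads: "The secondary endpoint would be to more accurately plan the resection of mandibular or maxillary bone if invasion is predicted". The second reads: "If invasion is not predicted based upon the imaging modalities, then the secondary endpoint would be to spare resection of uninvolved bone". The secondary objective in 2.2 is something else: "To compare the histopathologic findings to the radiologic findings".

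Section 5.4 gives each patient several readings: "All patients will received a helical CT, PET/CT and CBCT". Section 7.2 adds the clinical exam, MRI and any other modality used. It scores each against histology: "as compared to the histological examination of the specimens". It then adds: "In addition, the positive and negative predictive value will be calculated for each modality". Section 3.2 refers to a combination of modalities, but no section defines one.

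Four further places bear on this:

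- The Appendix says that imaging will be compared with histology of resected specimens.
- Section 6.1 has surgical planning done without knowledge of the CBCT result, and describes follow-up as adjuvant therapy and post-surgical care.
- Section 8.3 releases imaging results to the surgeon if a modality or combination is found accurate.
- Section 7.3 analyses all subjects who enrolled and consented.

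**The concern.** Sparing uninvolved bone is the patient benefit that 1.1 and 5.2 put forward, so a reader will look to 3.3 for evidence of it. Scoring that endpoint needs two things that the plan does not supply: a rule that turns several readings into predicted or not predicted, and proof that the bone left in place was free of tumour.

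The gap also reaches the main accuracy results. If a patient with a negative scan and no bone specimen enters the table as a true negative, specificity and negative predictive value rest partly on patients whose bone status nobody knows. Any missed invasion among them is absent from the false-negative count, which also flatters sensitivity. A statement that a negative scan makes sparing safe would draw on exactly these patients.

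**Working it through.** The plan has no figure of its own to reproduce here. The 20 subjects in the Study Summary come from case logs (7.1) and are not tied to this endpoint. The Appendix prints N=10, which is a separate matter; the counts below use 20.

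**Step 1. Can sparing be verified?**

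- The reference standard is histology of specimens (7.2), and the Appendix specifies resected specimens. Bone left in place gives no specimen. This is an inference from that wording, not an explicit statement. A partial resection gives histology only for the part removed.
- No section defines a recurrence endpoint, a follow-up duration or sampling of retained bone that could replace histology.
- Under 6.1 the surgeon plans without the CBCT result, so before the 8.3 unblinding a negative CBCT cannot itself lead to sparing.
- Section 7.2 has no variable or analysis for sparing or for planning accuracy.

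**Step 2. How is an unverified scan-negative patient classed?** The 7.2 definition asks for no histologic or radiographic evidence of invasion. It does not require that bone was examined. A patient without bone histology has no histologic evidence, so on a literal reading qualifies as a true negative, and 7.3 keeps that patient in the analysis.

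Take m scan-negative patients, of whom v have bone histology and all v are negative. The literal reading gives NPV = m/m = 100%. What the data support is a range from v/m (every unverified patient invaded) to 1 (none invaded). With m = 10 as an assumed number:

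| Verified v | NPV on literal reading | NPV supported by the data |
|---|---|---|
| 10 | 100% | 100% |
| 5 | 100% | 50% to 100% |
| 0 | 100% | 0% to 100% |

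**Step 3. Which branch does a patient enter?** Three binary readings give 2^3 = 8 patterns, of which 6 are discordant. The documents give no accuracies, so assume that each scan has sensitivity and specificity a. With independent errors, P(discordant) = 1 - a^3 - (1-a)^3. If half of the errors are shared by all scans, let h = (1-a)/2 and r = h/(1-h); then P(discordant) = (1-h)[1 - (1-r)^3 - r^3].

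| a | Independent errors | Half shared |
|---|---|---|
| 0.80 | 48% (9.6 of 20) | 27% (5.3 of 20) |
| 0.90 | 27% (5.4 of 20) | 14% (2.8 of 20) |
| 0.95 | 14% (2.9 of 20) | 7% (1.5 of 20) |

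The missing rule sets the size of the sparing branch. Assume 30% invasion, a = 0.80 and independent errors. The expected number of 20 patients classed as not predicted is then:

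- any positive scan counts as predicted: 20 × (0.3 × 0.008 + 0.7 × 0.512) = 7.2
- majority of scans: 20 × (0.3 × 0.104 + 0.7 × 0.896) = 13.2
- all scans must be positive: 20 × (0.3 × 0.488 + 0.7 × 0.992) = 16.8

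**The case against.** The best defence is that 3.3, read with 8.3, describes the hoped-for clinical use once a modality has proved accurate, and is only loosely called an endpoint. That is a plausible account of the intent. It does not rescue the text: 3.3 is the sole secondary endpoint, and if it is a hope it should be placed in the rationale.

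It is also fair to say that the counts proposed under the fix are largely the true-negative and false-negative cells that 7.2 already plans. That stands. What is new is the restriction to examined bone and the separate count of unverified patients.

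Three stronger readings are tempting, and the documents do not support them.

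- A reader might infer that patients with discordant scans fall outside both branches and are omitted. Predicted and not predicted are complements, so every patient belongs to one of them. What is missing is the rule that says which.
- A reader might infer that the plan credits missed invasions as successful sparing. Section 3.3 says uninvolved bone, so a missed invasion is not a success by its wording, and no section directs such a count. Nor is there a sound number for it. Assume sensitivity 0.80, specificity 0.85 and 30% invasion. For a single scan, missed invasions are 0.06/0.655 = 9.2% of scan-negatives, or 1.2 of 20 patients. If all three scans must be negative and errors are independent, the share is 0.0024/0.4323 = 0.6%. If half of the errors are shared, it is 0.3 × (0.10 + 0.90 × 0.111^3) = 0.0304 over 0.0304 + 0.7 × 0.925 × 0.919^3 = 0.533, or 5.7%. All of these treat every scan-negative patient as spared, which the masking in 6.1 rules out as a consequence of a CBCT reading before unblinding.
- A reader might infer that discordance is bound to be common. It falls to 7% at 95% accuracy with half of the errors shared, so no general threshold can be claimed.

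**Conclusion.** The point holds in this form: the design cannot verify bone sparing as 3.3 states it, and the definitions in 7.2 with the population in 7.3 allow unverified patients into the true-negative cell. Both parts rest on the wording of the documents and, for spared bone, on the inference that bone not resected is not examined.

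The size cannot be fixed from the documents, because they do not say how many enrolled patients will have bone histology. If all do, the true-negative problem disappears. If half of the scan-negative patients do not, the negative predictive value is bounded only between 50% and 100% even when every verified case is negative. The discordance and branch-size figures depend wholly on assumed accuracies and invasion rate, and serve only to show that the missing rule can matter. The study is small and descriptive with no planned test, so the consequence is a misleading claim about sparing, not a wrong test decision.

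**What to change.** Restate 3.3 as an endpoint scored separately for each modality, limited to patients whose bone was resected and examined, and reword 2.2 to match. For each modality report, always together:

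- (a) potentially avoidable resections: scan negative, histology negative
- (b) missed invasions: scan negative, histology positive
- separately, the number of scan-negative patients without bone histology

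State that (a) and (b) are the true-negative and false-negative cells of 7.2 in verified patients, and that they describe potential sparing, not sparing achieved. Make clear in 7.2 that a patient without bone histology is not a true negative. Score any combination of modalities in the same way, under a rule fixed before the data are read. The first branch of 3.3, on planning the resection, also has no variable in 7.2; give it one or move it to the rationale.

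The cost is wording in 2.2, 3.3 and 7.2 and one table, with no change to patient care. The downside is that the endpoint covers only patients with examined bone, and missed invasion in spared bone stays unseen; the separate count shows how many patients that could affect.

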3.4 Primary Safety Endpoints

As this study compares radiologic modalities of diagnosis that are currently used for standard of care practice, there is no safety risk.

4.0 SUBJECT SELECTION AND WITHDRAWAL

4.1 Inclusion Criteria

- Age 18-90
- Diagnosis of squamous cell carcinoma of the oral cavity
- Able to read and sign and informed consent

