1.1 Specific Aims and Hypothesis

There are newer imaging modalities that have not been studied sufficiently to determine whether intraoral SCC has or has not infiltrated a segment of the mandible or maxilla, necessitating partial or complete resection of the jaw. One such modality is cone beam CT (CBCT), which delivers approximately 1/6 the amount of radiation and is about 1/10 the cost of a multi-slice, helical CT¹. A previously published imaging protocol by Van Cann et al² used MRI, CT and bone SPECT to image the mandible. In contrast to the prior algorithm, this study aims to test newer modalities such as the CBCT, PET/CT and helical CT against more traditional imaging techniques, to attempt to detect neoplastic infiltration of the mandible and maxilla. We hypothesize that CBCT or a combination of the aforementioned modalities can be used in order to more accurately predict invasion of the maxilla or mandible by intraoral SCC.

The accurate prediction of the presence or absence of malignant invasion of the jaws greatly influences the surgical treatment plan. This is important for several reasons. First, it may change the staging of the disease, necessitating a more or less involved resection and reconstruction. Second, this knowledge will greatly benefit the surgeon, since the reconstruction of an extensive surgical defect will be more complex and require greater planning. In addition, occult infiltration of the jaws may be a source of locoregional regrowth and recurrence that may be detectable by such imaging, leading to a wider, more appropriate and oncologically sound resection. Third, if absence of mandibular or maxillary invasion can be proven statistically, it will permit “sparing” of complete or partial resection. Thus, the mandible and maxilla, which are critical to facial form and function, will be preserved in some form and improve the overall quality of life of the cancer patient.

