4.2 Exclusion Criteria

- prior mandibular surgery,
- primary intraosseous carcinoma,
- prior history of radiation to the mandible,
- obvious finding of clinical invasion of the mandible

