4.3 Gender/Minority/Pediatric Inclusion for Research

All ethnicities will be included in this study of both male and female gender. The patients will be adults, 18 years of age or older and have a biopsy proven squamous cell carcinoma of the oral cavity.

While men have an increased incidence of oral SCC by 2:1 as compared to women, there will be no preference for one gender or another. Also, the ratio of men: women in the study will be monitored and all patients that meet the inclusion criteria will be added regardless of gender

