15.0 APPENDICES

To be posted in OMFS and JHNS office:

Prediction of Bone Invasion by Squamous Cell Carcinoma:

Inclusion: SCC of the oral cavity

Exclusion:

1. prior mandibular surgery
2. primary intraosseous carcinoma
3. prior history of radiation to the mandible
4. obvious finding of clinical invasion of the mandible,
5. age under 18 years old

Visit I: Screening visit

Visit II: Referral to OMS department for CBCT

Visit III: Definitive Surgical Treatment Plan

Goal:

To determine if any imaging modalities or combination of studies can accurately predict the presence or absence of maxillary or mandibular invasion by oral SCC. The diagnostic imaging will be compared to the histologic investigation of the resected specimens in order to determine their accuracy.

Patient Cohort
(N=10)

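### Any oral cavity SCC can enter and all are pooled, so tumours away from the jaw can count as true negatives and raise specificity and NPV through case mix alone

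*Combined protocol and SAP*

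**What the plan says.** The tumour criterion in section 4.1 is "Diagnosis of squamous cell carcinoma of the oral cavity". The card posted in the clinics (section 15.0) has "Inclusion: SCC of the oral cavity", and the synopsis and section 4.3 say the same. None of them asks that the tumour touch or lie near the jaw, or that bone resection be under consideration. Section 4.3 adds that "all patients that meet the inclusion criteria will be added regardless of gender". The one criterion that concerns bone involvement is an exclusion in section 4.2: "obvious finding of clinical invasion of the mandible".

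Section 7.2 compares each modality with histology and defines true negatives as patients "pts without histologic or radiographic evidence of" invasion. Specificity, PPV and NPV come from the resulting counts. Section 7.3 analyses every consented, enrolled subject, with no stratum by tumour site.

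On purpose, section 1.1 says that "if absence of mandibular or maxillary invasion can be proven statistically, it will permit" the sparing of resection, and section 3.3 makes sparing uninvolved bone a secondary endpoint.

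**The concern.** The trial's question arises in patients whose tumour might have reached bone. In a patient with a soft-tissue tumour well away from the jaw, no modality would be expected to show invasion and no bone decision depends on the scan. Such a patient is eligible. Section 4.4 also gives a reason to image that does not depend on tumour site, since CBCT serves the dental assessment before possible radiotherapy.

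If these patients enter the pooled table as true negatives, specificity and NPV partly describe the mix of tumour sites at this centre. A reader using the NPV to judge a negative scan in a patient whose tumour abuts bone would be given a figure that is too favourable. Modalities would also look more alike on these two percentages, and comparing modalities is the primary objective (section 2.1).

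**Working it through.** **The plan's own figures.** The synopsis gives 20 subjects. Section 7.1 bases this on yearly case volume, with no target accuracy, precision or prevalence, so there is nothing to reproduce. (The appendix cohort box reads N=10; that needs reconciling separately.) The documents state no site mix, invasion prevalence or accuracy. Every rate below is an assumption.

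**Step 1: how a remote tumour is classified.** The reference standard is histology of the resected specimens (sections 7.2 and 15.0). A patient with no jaw resection has no bone specimen. Two readings are open:

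- Reading A: with no histologic and no radiographic evidence of invasion, the patient meets the 7.2 wording and counts as a true negative. Section 7.3, which analyses everyone enrolled, points this way.
- Reading B: the patient is unverified and drops out of the table. Nothing is inflated, but places among the 20 are used up.

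The protocol does not choose. Steps 2 to 4 apply under reading A, or where remote tumours do have negative bone histology.

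**Step 2: worked counts.** Assume 12 bone-adjacent tumours, 4 invaded and 8 not, then add remote tumours that are all read negative. Sensitivity = TP/(TP+FN); specificity = TN/(FP+TN); PPV = TP/(TP+FP); NPV = TN/(TN+FN).

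| Set | TP | FN | TN | FP | Sensitivity | Specificity | PPV | NPV |
|---|---|---|---|---|---|---|---|---|
| 12 adjacent | 3 | 1 | 6 | 2 | 3/4 = 75% | 6/8 = 75% | 3/5 = 60% | 6/7 = 85.7% |
| plus 4 remote | 3 | 1 | 10 | 2 | 75% | 10/12 = 83.3% | 60% | 10/11 = 90.9% |
| plus 8 remote | 3 | 1 | 14 | 2 | 75% | 14/16 = 87.5% | 60% | 14/15 = 93.3% |

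The scan's results in the adjacent tumours are the same in every row.

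**Step 3: range.** Let f be the share of remote tumours (none invaded, specificity Sp_e), and p, Se and Sp the prevalence, sensitivity and specificity in adjacent tumours. Then, per subject enrolled:

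- TN = (1−f)(1−p)Sp + f·Sp_e
- Specificity = TN / [(1−f)(1−p) + f]
- NPV = TN / [TN + (1−f)p(1−Se)]

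With p = 0.30, Se = Sp = 0.80, Sp_e = 1 and f = 0.5: TN = 0.5×0.7×0.8 + 0.5 = 0.78; specificity = 0.78/0.85 = 91.8%; NPV = 0.78/(0.78+0.03) = 96.3%. Across f:

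| f | Specificity | NPV | Expected invaded cases of 20 |
|---|---|---|---|
| 0 | 80.0% | 90.3% | 6.0 |
| 25% | 86.5% | 93.7% | 4.5 |
| 50% | 91.8% | 96.3% | 3.0 |
| 75% | 96.2% | 98.3% | 1.5 |

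At f = 50%, over p 0.3 and 0.5, Se/Sp from 0.8/0.7 to 0.9/0.9 and Sp_e 0.95 and 1, specificity rises by about 3 to 20 points and NPV by about 3 to 15. Specificity rises whenever remote tumours are read correctly more often than adjacent non-invaded ones. PPV is unchanged if every remote tumour is read negative and falls otherwise (from 63.2% to 55.8% in the case above with Sp_e = 0.95).

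**Step 4: differences between modalities.** Two modalities at 6/8 and 7/8 in adjacent tumours differ by 12.5 points in specificity. With 8 remote negatives each, 14/16 and 15/16 differ by 6.25.

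**The case against.** The strongest reply is that inflation depends on reading A. A reader might infer that the plan necessarily inflates specificity and NPV; the documents do not support that, because they never say how a patient without bone histology is classified. This stands, and the point is conditional on it. The silence is itself part of the gap.

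A reader might also infer that specificity is the figure offered to justify leaving bone in place. Section 1.1 speaks only of statistical proof of absence and names no measure. Specificity describes false positives; whether a negative scan can be relied on depends on missed invasion, that is, on NPV and sensitivity. Sensitivity is untouched by remote tumours, so only the NPV part bears directly on sparing.

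A third tempting reading is that excluding obvious mandibular invasion makes the cohort the reverse of one enriched for doubt. It does not: that exclusion moves the cohort toward doubtful cases, and it leaves obvious maxillary invasion eligible. Only the low-risk end is unrestricted.

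Sampling error is large beside the shift: exact 95% intervals are about 35–97% for 6/8 and 62–98% for 14/16, and about 42–99.6% for NPV 6/7 and 68–99.8% for 14/15. That limits the practical weight, but an interval around a pooled figure does not correct for case mix.

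On comparisons, every patient is due all three scans (section 5.4), so cases on which the modalities agree leave paired discordant counts unchanged. The shrinkage affects the separate percentages, which are what section 7.2 reports.

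Finally, narrowing entry by examination is not clearly better, because the clinical exam is itself one of the tests assessed in section 7.2, and section 1.1 wants occult infiltration found.

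**Conclusion.** The concern holds in conditional form. Entry is open to any oral cavity SCC, all enrolled subjects are pooled, and the true-negative wording admits a patient with a tumour away from the jaw and no bone specimen. If such patients are counted that way, specificity and NPV rise with their share, and differences between modalities in those two percentages shrink. Sensitivity does not change.

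The size cannot be derived from the documents. The move from 75% to 88% in specificity and from 86% to 93% in NPV rests on assumed counts, with 8 of 20 tumours remote and all read negative. The text does not support a claim that inflation is certain, of known size, or a reason that entry must be restricted. It does justify an inexpensive correction to data collection and to the analysis set.

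**What to change.** Leave sections 4.1 and 4.2 as they are on this point, and change three things.

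1. In section 6.1 and on the case report form, record tumour subsite and adjacency to the mandible or maxilla at screening, before any study scan is read.
2. In sections 7.2 and 7.3, state that the primary specificity, PPV and NPV use bone-adjacent tumours with a bone histology result, with all-enrolled figures as secondary.
3. In section 7.2, state that a patient without bone histology is reported separately, by modality reading, and is not counted as a true negative in either set.

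The cost is one screening item and a few sentences; no patient is lost from enrolment. The primary figures will rest on fewer subjects and be less favourable: in the illustration, specificity rests on 8 non-invaded tumours where the pooled table has 16. Because adjacency is judged partly on examination, restricting to adjacent tumours alters the measured accuracy of the clinical exam, so that accuracy should also be shown in all enrolled patients with bone histology.
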